Section to be changed		6.2.1 Baseline (group 1)
Description of change		1. Adding a description of the timepoint when the roll over decision can be made 2. Adding a wording for cases when the interruption between the trial is longer than 7 days. 3. replace randomization by enrollment
Rationale for change		1. To clarify that the latest timepoint for roll over decision can also be EOT of 1293.10 2. To clarify that in case of longer interruption certain lab parameters shall be taken as baseline for 1293-0013 3. To adapt to group 1 (with no randomization)
Section to be changed		6.2.2. Treatment period
Description of change		1. Removing reference to group 2 2. Adding a wording on treatment interruptions
Rationale for change		1. Group 2 was cancelled 2. To clarify that the CTL shall be informed about longer treatment interruptions.
Section to be changed		6.2.3.3. Additional follow-up for prematurely discontinued patients
Description of change		Adding a wording regarding follow up visit intervals
Rationale for change		To clarify when early discontinued patients shall come for follow up visits
Section to be changed		7.1 Statical design - model

Description of change		Modified design description to highlight important features of the Group 1-only trial
Rationale for change		Group 2 was cancelled
Section to be changed		7.2 Null and Alternative Hypotheses
Description of change		Further description/justification of statistical approach added.
Rationale for change		To more clearly describe how the statistical testing addresses the trial objectives.
Section to be changed		7.3. Planned analysis
Description of change		1. Analyses will incorporate data from 1293.10. 2. Baseline for 1293-0013 is defined as the baseline from 1293.10 unless otherwise indicated. 3. Baseline characteristics for patients who enter 1293-0013 (Group 1) will be compared to baseline characteristics for the treated population of 1293.10. 4. Population data set defined as ITT.
Rationale for change		1 & 2. With cancellation of Group 2, the analysis focus can be the long term (two-year) efficacy and safety assessment for the Group 1 patients. 3. Any relevant shifts in baseline characteristics could affect interpretation of results & should be noted. 4. Approach will be to consider discontinued patients as failures & include in analysis of the primary endpoint.
Section to be changed		7.3.1 Primary endpoint analysis
Description of change		1. Population data set defined as ITT. 2. Descriptions of Group 2 analyses removed. 3. Statistical methods in 1293.10 will be used in 1293-0013. 4. Removed analyses by ethnicity and race.
Rationale for change		1. Approach will be to consider discontinued patients as failures & include in analysis of the primary endpoint. 2. Group 2 cancelled. 3. For consistency/comparison with 1293.10 results 4. Small numbers of patients per treatment group.
Section to be changed		7.3.2 Secondary endpoint analysis
Description of change		Simplified analysis plan for time to first renal flare by removing hazard ratio & 95% confidence interval.

Rationale for change		Numbers of renal flares to date are small. Plan to present Kaplan Meier curve should be adequate.
Section to be changed		
Description of change		
Rationale for change		
Section to be changed		7.3.4 Safety analyses
Description of change		1. Added that analysis of AEs will be based on randomised treatment. 2. Analysis of AESIs and additional SAE rule for Japan mentioned.
Rationale for change		More complete specification of analysis and for consistency with Section 5.2.
Section to be changed		7.4 Interim Analyses
Description of change		Deleted reference to an interim analysis
Rationale for change		Due to cancellation of group 2, the previously specified interim analysis after completion of Group 1 is now the final analysis of the trial.
Section to be changed		7.5 Handling of missing data
Description of change		1. Added text to indicate that the ‘non-completers considered failure’ approach is only for CRR-related endpoints 2. Removed statement that no imputation will be performed for all other endpoints.
Rationale for change		1. Correction to previous specification 2. Need for imputation of other endpoints will be assessed during data review. If there are significant numbers of patients with missing data, imputation techniques may be considered & specified in the TSAP.
Section to be changed		7.6 Randomisation
Description of change		Removed description of the randomisation of Group 2 patients.
Rationale for change		Group 2 is cancelled.
Section to be changed		7.7 Determination of samples size

Description of change		Removed references to Group 2 including references to sample size calculations, assumptions and expected power for Group 2. Also removed discussion of number(s) of doses to be studied in Group 2.
Rationale for change		Group 2 was cancelled

2. LIST OF ABBREVIATIONS

Term	Definition / description
ACEi	Angiotensin-converting enzyme inhibitor
AE	Adverse event
AESI	Adverse events of special interest
ARB	Angiotensin receptor blocker
Anti-dsDNA	Anti-double stranded DexoxyriboNucleic Acid
AUC	Area under the curve
BI	Boehringer Ingelheim
C3	Complement Component C3
C4	Complement Component C4
CD	Cluster of Differentiation
CMH	Cochran-Mantel-Haenszel
CRR	Complete Renal Response
CTC	Common Terminology Criteria
CTP	Clinical Trial Protocol
CTR	Clinical Trial Report
DMC	Data Monitoring Committee
ECG	Electrocardiogram
eCRF	electronic Case Report Form
eGFR	estimated Glomerular Filtration Rate
EMA	European Medicines Agency
EOS	End of study
EoT	End of text
EOT	End of trial
FACIT-F	Functional Assessment Chronic Illness Therapy-Fatigue
FU	Follow Up
GFR	Glomerular Filtration Rate
h	hour
HRQoL	Health Related Quality of Life
IA	Interim analysis

Proprietary confidential information © 2021 Boehringer Ingelheim International GmbH or one or more of its affiliated companies

Term	Definition / description
ICH	International Conference on Harmonisation
iPD	important Protocol Deviation
IRT	Interactive Response Technology
ITT	Intent To Treat
IV	Intravenous
KOL	Key Opinion Leader
LLN	Lower limit of normal
LLOQ	Lower limit of quantification
LN	Lupus Nephritis
MedDRA	Medical Dictionary for Regulatory Activities
min	minute
MQRM	Medical Quality Review Meeting
MRR	Major Renal Response
ms	millisecond
PCSA	Possible clinically significant abnormality
PPS	Per protocol set
PR	Time interval of ECG
PRR	Partial Renal Response
PT	Preferred term
RCTC	Rheumatology Common Toxicity Criteria
REP	Residual effect period
RPM	Report Planning Meeting
QRS	Time interval of ECG
QT	Time interval of ECG
SAS	Statistical Analysis System (SAS® System, [REDACTED], [REDACTED])
SD	Standard deviation
SELENA	Safety of Estrogens in Lupus National Assessment
SF-36	36-Item Short-Form Health Survey
SLE	Systemic Lupus Erythematosus

Proprietary confidential information © 2021 Boehringer Ingelheim International GmbH or one or more of its affiliated companies

Term	Definition / description
SLEDAI	SLE Disease Activity Index
SOC	System organ class
TOC	Table of contents
TSAP	Trial statistical analysis plan
UP	Urine protein
UC	Urine creatinine
WBC	White blood cell
WHO-DD	World Health Organization-Drug dictionary

3. INTRODUCTION

The purpose of this document is to provide a more technical and detailed elaboration of the principal features of the analysis than was described in the protocol, and to include detailed procedures for executing the statistical analysis of the primary and secondary endpoints and other data.

This TSAP assumes familiarity with the Clinical Trial Protocol (CTP), including Protocol Amendments. In particular, the TSAP is based on the planned analysis specification as written in CTP Section 7 “Statistical Methods and Determination of Sample Size”. Therefore, TSAP readers may consult the CTP for more background information on the study, e.g., on study objectives, study design and population, treatments, definition of measurements and variables, planning of sample size, randomization.

SAS[®] Version 9.4 (or later version) will be used for all analyses.

4. CHANGES IN THE PLANNED ANALYSIS OF THE STUDY

With Amendment #2 to the CTP (21-Dec-2020), Group 2 was cancelled. Group 2 was to be a cohort of patients who achieved a meaningful response to induction treatment outside of 1293.10. With all patients in 1293.13 now coming from trial 1293.10 (Group 1), the sole focus in 1293.13 can be long-term (now 2-year) assessment of their induction and continued maintenance therapy in 1293.13. Efficacy and safety tables and figures will include data from 1293.10 for assessment of BI655064 doses versus placebo over this 2-year treatment period.

Amendment #2 describes the unblinding of treatment codes for 29 patients (20 on treatment and 9 in follow-up) in the trial on 20-Oct-2020. At that time, the investigator was asked to discuss with the patient their treatment options and continued participation in 1293.13. It is not expected that this partial unblinding introduced meaningful reporting bias. The primary endpoint and most of the secondary endpoints are derived from laboratory measurements. With respect to the SLEDAI, most domains are lab-based and other domains are examination findings. No analyses to address potential bias are planned.

The CTP list of secondary and further endpoints was reviewed (prior to release of treatment codes) resulting in some additions and a few deletions essentially driven by learnings from the 1293.10 trial. [Section 5.2](#) lists the secondary endpoints noting the addition of one endpoint (proportion of patients with partial renal response (PRR) without renal flare) inadvertently left off the CTP list of secondary endpoints (but specified in another section) and one deletion with explanation for the deletion (proportion of patients with CRR at Week 52). [REDACTED]

Important Protocol Deviations (iPDs) were updated during trial conduct to reflect learnings and input from Key Opinion Leaders (KOLs). The Per protocol set (PPS) was dropped with the second CTP amendment.

Sensitivity, subgroup and exploratory analyses added to the TSAP for the primary endpoint are listed in [Sections 7.4.2](#). Sensitivity, subgroup and exploratory analyses were also added to the TSAP for an important secondary endpoint; these are listed in [Sections 7.5.2](#).

The biomarker analysis will be outlined outside of this TSAP.

[REDACTED]

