6. GENERAL ANALYSIS DEFINITIONS

6.1 TREATMENTS

For reporting purposes, all patients will be classified into one of the following treatment groups as determined by random treatment assignment at the start of 1293.10:

Sort order	Treatment	Long label	Short label
01	B	BI 655064 120mg	BI 120mg
02	C	BI 655064 180mg	BI 180mg
03	D	BI 655064 240mg	BI 240mg
04	A	Placebo	Placebo

These will be the default labels and sort order for reporting the treatment groups.

The following study periods based on actual start and stop dates of study treatment administration are defined:

Treatment: start date of randomised to double-blind medication in 1293.10 to date of last dose in 1293.13

Follow-up: day after the last dose of randomised double-blind medication in 1293.13 through trial completion and after trial completion

Rules for assigning AEs/laboratory data to the study periods are as follows.

AEs/laboratory data will be assigned to the treatment period if they occur/samples were taken after the first injection of study medication to the date of last administration of study medication plus 50 days.

Adverse events with onset on or after the 51st day after the last administration of trial medication will be considered 'Follow-up' events.

Laboratory data on or after the 51st day after the last administration of trial medication will be considered 'Follow-up' data.

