7.7 EXTENT OF EXPOSURE

Duration of time on treatment starting with the first injection in 1293.10 to the last injection in 1293.13 will be derived for each patient & summarized by treatment group.

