7.8 SAFETY ANALYSIS

All safety analyses will be performed on the treated set and performed in accordance with BI standards. Tabulations of frequencies/proportions will be used for the evaluation of categorical (qualitative) data, and tabulations of descriptive statistics will be used to analyse continuous (quantitative) data.

The format of the listings and tables will follow the BI guideline ‘Reporting of clinical trials and project summaries’ (3).

The individual values of all subjects will be listed, sorted by treatment, subject number and visit. The listings will be contained in Appendix 16.2.

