7.8.1 Adverse events

AEs will be analysed using BI standards, as described in the guideline, ‘Handling and summarization of adverse event data for clinical trial reports and integrated summaries’ (4).

Unless otherwise specified, the analyses of adverse events will be descriptive in nature. All analyses of AEs will be based on the number of patients with AEs and NOT on the number of AEs.

The analysis of AEs will be based on the concept of treatment emergent AEs. This means that all AEs occurring between first drug intake and end of the residual effect period (REP) will be assigned to the randomised treatment. The residual effect period is defined as 50 days. All AEs occurring before first drug intake will be assigned to ‘Screening’ and all AEs occurring after last drug intake + 50 days will be assigned to ‘Follow-up’ (and presented in listings only). For details on the treatment definition, see [Section 6.1](#)

According to ICH E3 (5), in addition to Deaths and Serious Adverse Events, ‘other significant’ AEs need to be listed in the clinical trial report. These will be any non-serious adverse event that led to an action taken with study drug (e.g. discontinuation or dose reduced or interrupted).

Proprietary confidential information © 2021 Boehringer Ingelheim International GmbH or one or more of its affiliated companies

An overall summary of adverse events will be presented. The frequency of patients with adverse events will be summarised by treatment, primary system organ class and preferred term. Separate tables will be provided for patients with adverse events leading to treatment discontinuation, other significant adverse events according to ICH E3 (5), related adverse events and serious adverse events. AEs will also be summarised by maximum RCTC grade.

Adverse events of special interest (AESI) will be presented in tables and listings for the following:

- Injection site reactions and hypersensitivity, including anaphylaxis reaction
- Malignancies, lymphoproliferative disorders
- Severe infections and opportunistic infections
- Thromboembolism (Thrombosis and adjunct immunosuppression)
- Cytokine release syndrome
- Drug induced liver injury (DILI) (if applicable)

The system organ classes will be sorted by frequency, PTs will be sorted by frequency (within SOC).

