7.8.2 Laboratory data

The analyses of laboratory data will be descriptive in nature and will be based on BI standards (6).

The residual effect period of 50 days will be applied to the laboratory data. Laboratory data will be assigned to the treatment period if samples were taken after the first injection of study medication to the date of last administration of study medication plus 50 days. Laboratory data from samples taken on or after the 51st day after the last administration of trial medication will be considered 'Follow-up' data.

Tables and figures in Section 15 of the CTR will include laboratory data from the treatment period; data from the follow-up period will not be included. Listings of laboratory data will display on-treatment and follow-up data, with follow-up data flagged to identify they are from samples taken during the follow-up period.

Possibly clinically significant abnormalities (PCSA) were identified using BI standard rules plus RCTC.

Figures displaying mean and median WBC and neutrophils over time will be provided.

Descriptive statistics for anti-dsDNA, C3 and C4 counts over time will be displayed for all patients in the treated set. For anti-dsDNA, descriptive statistics for patients who are positive at baseline [i.e., >ULN (=75 IU/mL)] will be tabulated and displayed in a figure. For C3 and C4, patients who are below lower limit of normal (LLN) at baseline will be tabulated and displayed in figures. LLN for C3 is 0.9 g/L. LLN for C4 is 0.1 g/L.

Descriptive statistics over time for erythrocytation rate will be provided.

Proprietary confidential information © 2021 Boehringer Ingelheim International GmbH or one or more of its affiliated companies

IgG & IgM values will be listed by treatment, patient and visit. Values outside the normal range will be flagged. Possibly clinically significant abnormalities will be flagged.

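### The two-year dose-versus-placebo safety tables appear to cover only roll-over patients, so for deaths and discontinuations due to adverse events they show in effect the second year only

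*SAP*

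**What the plan says.** SAP section 4 explains that, with Group 2 cancelled, "the sole focus in 1293.13 can be long-term (now 2-year) assessment of their induction and continued maintenance therapy in 1293.13". It then commits the efficacy and safety displays to that span: "Efficacy and safety tables and figures will include data from 1293.10 for assessment of BI655064 doses versus placebo over this 2-year treatment period".

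The technical sections follow suit:

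- SAP 6.1 defines the period as "Treatment: start date of randomised to double-blind medication in 1293.10 to date of last dose in 1293.13".
- SAP 7.7 derives exposure as "Duration of time on treatment starting with the first injection in 1293.10 to the last injection in 1293.13".
- SAP 7.8.1 has "all AEs occurring between first drug intake and end of the residual effect period (REP) will be assigned to the randomised treatment", with a residual effect period of 50 days. It adds: "Separate tables will be provided for patients with adverse events leading to treatment discontinuation". Serious adverse events also get their own table.
- SAP 7.8 sets the population: "All safety analyses will be performed on the treated set".

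SAP 6.3 defines the treated set by at least one dose of investigational treatment and does not say in which trial. Protocol 7.3 equates the treated set with patients treated in 1293-0013, but in the sentence on the primary analysis; its safety sentence refers only to all treated patients. The same section plans a descriptive comparison of safety between the experimental arms and control.

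**The concern.** The clock starts at randomised treatment in 1293.10, but a patient appears to enter the tables only by reaching 1293-0013. Year 1 is then guaranteed survival time, and nearly guaranteed time on drug, for everyone in the table. It supplies exposure but no deaths and almost no permanent discontinuations due to adverse events, which are events that a dose-versus-placebo safety table should show.

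A reader who sees a two-year treatment period and a percentage of patients stopping for adverse events will take it as a two-year risk. It is closer to the risk over 1293-0013 among patients who had already tolerated a year. If one dose caused more early stopping, the patients concerned are not in the table and the arm looks no different from placebo. Protocol 3.2 says that this trial, together with 1293.10, is meant to inform the choice of dose regimens for Phase III, so how these tables read across arms matters.

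**Working it through.** The plan gives no event count, rate or power figure for safety, so there is no stated figure to reproduce. The check is first logical, then illustrative.

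**Step 1: who is in the tables.** Four passages point to roll-over patients only:

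- SAP 4 speaks of the induction and maintenance therapy of the 1293.13 patients.
- Protocol 7.3 ties the treated set to 1293-0013.
- The rationale for the Protocol 7.3 change in Global Amendment 2 refers to Group 1 patients.
- The SAP 6.1 period and the SAP 7.7 exposure both end at a last dose in 1293.13, which does not exist for a patient who never rolled over.

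If SAP 6.3 did mean everyone treated in 1293.10, the period and exposure rules would be undefined for those who did not continue. Either way the text needs an edit.

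**Step 2: what entry excludes.** Protocol 3.3.2 requires CRR, PRR, or proteinuria of at most 1 g/d (or UP/UC at most 1) at the end of 1293.10. Protocol 6.2.1 places Visit 1 on the day of the 1293.10 end-of-treatment visit or within 3 days. Protocol 4.1.4 allows longer gaps only for administrative reasons, with approval. Year-1 deaths are therefore impossible in this set. Permanent year-1 discontinuations due to adverse events are nearly so; this second point is a strong inference, because no criterion literally requires being on drug at that visit. Year-1 events that did not end treatment remain counted.

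**Step 3: share of exposure before Visit 1.** Inputs are 52 weeks in 1293.10, 52 weeks in 1293-0013 and about 60 roll-over patients (Protocol 7.7).

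- Completer: 364 / (364 + 364) = 364/728 = 50%.
- Patient stopping at Week 26 of 1293-0013: 52/78 = 67%.
- All patients: 60 × 52/52 = about 60 patient-years.

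**Step 4: effect on percentages (illustration).** Assume the same annual risk r of a treatment-ending event in both years. The risk for starters followed and treated for two years is 1 − (1 − r)². The roll-over table shows about r.

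| r (assumed) | Two-year risk | Shown | Share of events missing | Patients per assumed arm of 15 |
|---|---|---|---|---|
| 5% | 9.75% | 5% | 4.75/9.75 = 48.7% | 0.71 |
| 10% | 19.0% | 10% | 9.0/19.0 = 47.4% | 1.35 |
| 20% | 36.0% | 20% | 16.0/36.0 = 44.4% | 2.40 |

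**Step 5: effect on the contrast between arms (illustration).** With 5% v 10% in both years, the two-year ratio is 19.0/9.75 = 1.95 and the displayed ratio is 10/5 = 2.0, so almost nothing is lost. Now put the excess in year 1: 5% on placebo, 10%, 15% or 20% on active, and 5% in both arms in year 2. The two-year risk on active is 1 − (1 − a)(0.95) = 14.5%, 19.25% or 24.0%, against 9.75% on placebo. The differences of 4.75, 9.5 and 14.25 points would all display as 0.

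**The case against.** The strongest reply is that the year-1 comparison belongs to 1293.10, where it is randomised and has been analysed, and that roll-over percentages are correct for the roll-over population. Safety here is descriptive, without hypothesis tests, and at the assumed rates the missing events come to about one to two patients per arm. SAP 7.4.1 already warns that entry required response in 1293.10, and Protocol 7.3 plans to compare baseline characteristics of entrants with those of the 1293.10 population. Individual values are listed by visit, so timing can be recovered. All of this lowers the weight of the point. It does not remove it: the 7.4.1 caveat sits in the efficacy section, a baseline comparison shows no lost events, and the tables are expressly for comparing doses with placebo over two years.

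Several stronger readings are tempting and are not supported:

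- **Rates are halved.** Event rates per patient-year over the SAP 6.1 period would be about half the 1293-0013 rate. With hazard L = −ln(1 − r) and r = 10%, that is 5.13 v 10.54 per 100 patient-years. But SAP 7.8.1 counts patients with events and the visible SAP plans no such rate; this arises only if one is formed.
- **Laboratory tables are distorted.** SAP 7.8.2 uses the same clock ("Laboratory data will be assigned to the treatment period if samples were taken after the first injection of study medication"), but the mechanism concerns events that end treatment, and no laboratory effect is shown.
- **The comparison favours the drug.** The direction is unknown, because losses by arm in 1293.10 are not given.
- **The safety clock should restart at Visit 1.** That would drop on-drug year-1 events from the main tables and recover no year-1 excess, since the Visit 1 cohort is equally selected. Nor can events ongoing at Visit 1 become baseline conditions through Protocol 7.3.4: its rule on worsening concerns events that began before first drug intake, and these generally began on drug.

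The population remains an inference. SAP 6.4, 7.6 and 10 are not visible, and the internal table guidelines that the SAP cites are not among the documents.

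**Conclusion.** The point holds as one of presentation and interpretation. On the best reading of the population, the two-year tables can show no year-1 deaths and almost no year-1 permanent discontinuations due to adverse events, so for these events their percentages describe 1293-0013. If risk is equal in the two years, roughly half the two-year events are absent (44% to 49% at assumed annual risks of 20% to 5%) and the ratio between arms barely changes. The contrast is lost where the excess lies in year 1. The 50% share of a completer's exposure follows from the documents; the event risks and 15 patients per arm are assumptions. Neither the primary efficacy analysis nor any error rate is affected.

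**What to change.** Keep the two-year roll-over adverse event tables, and change four things:

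1. Split them by trial period (1293.10 and 1293-0013), keeping events that began on drug in 1293.10 as on-treatment events.
2. For deaths, adverse events leading to discontinuation and serious adverse events, add a companion table of all patients treated in 1293.10, by randomised arm. Follow each patient to the last dose in either trial plus 50 days, and show the number rolled over and the exposure by arm.
3. Label the roll-over tables as conditional on year-1 response and roll-over.
4. Name the trial in each set definition in SAP 6.3.

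The cost is a few extra tables and the use of 1293.10 data on patients who did not roll over. Those patients contribute at most about one year, so follow-up is unequal. The companion table describes the whole programme and does not estimate the two-year risk formula used above; the exposure columns make that visible. Items 3 and 4 are text changes only.
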